8.4 Inclusion Criteria

Participants must meet ALL of the following criteria:

1. Individuals presenting with pain in superficial soft tissue, such as ankle, back, knee, wrist, elbow, shoulder, foot, or neck pain, or minor muscular and joint aches and pains associated with over exertion, strains, sprains, or arthritis
2. Prescribed use of the OrthoCor Active System or Standard of Care (SOC) intervention
3. Willing and able to provide informed consent or obtain consent from legal authorized representative (LAR)

8.5 Exclusion Criteria

Participants must not meet ANY of the following criteria:

1. Have a cardiac pacemaker, cardioverter defibrillator, neurostimulator, infusion pump or any active medical implant
2. Have an implanted metallic lead or any type of wire coil implant, or any implanted system that may contain lead
3. Current or expected use of opioids
4. Who are or may be pregnant
5. Have an open wound at the area of application
6. Are not capable or fully aware to the sensation of heat
7. Have poor circulation or heart disease
8. Have diabetes
9. Under the age of 18 or individuals with open bone growth plates
10. Unable to provide consent or obtain consent from a LAR
11. Unwilling or unable to use the OrthoCor Active System or Standard of Care (SOC) intervention
12. Unwilling or unable to complete the daily pain assessment
13. Enrolled in a study to evaluate an investigational drug
14. Prisoner or under incarceration

9.0 SUBJECT PARTICIPATION AND STUDY DURATION

Potential study subjects are males and females presenting to the designated study sites with pain in superficial soft tissue, such as in the ankle, back, knee, wrist, elbow, shoulder, foot, or neck who are prescribed the use of the OrthoCor Active System or Standard of Care (SOC) intervention. This will be a one-time on-site visit with data collection for 14 days.

All study participants will have the opportunity to continue in the research extension with data collection for another 14 days. Participation in the exploratory extension is optional.

9.1 Site selection Criteria

The trial will be conducted at up to five (5) sites. The sites will be selected by the CRO and agreed upon by the Sponsor.

- The institution/collection site must have access to the necessary equipment and supplies that are needed for the study and for study data collection.
- Clinical research study experience and resources that demonstrate good compliance with study requirements and timely, complete documentation of subject visits.
- Investigative team should designate a study coordinator to manage the study.
- Ability to adhere to the standards of Good Clinical Practice (GCP) and ICH E6(R2).
- Agree to comply with data collection requirements and data entry timelines.
- Study site will respond to queries from CRO, Caerus Corporation (or designee) in a timely manner.
- Willingness to allow personnel from CRO, Caerus Corporation (or designee) access to, Investigator's study records, data, and subject files as they pertain to the study.

9.2 Screening Process

Subjects will be prescreened for eligibility and if qualified will be approached with the study information and asked if they are willing to participate.

Informed consent will be obtained per section 14.2. All patients who sign a consent form are considered study subjects. A study participant is considered enrolled after they have signed an informed consent form and after the inclusion/exclusion criteria have been met.

After an IRB approved Informed Consent Form is obtained and study inclusion/exclusion criteria are met, the study assessment will begin immediately.

9.3 Baseline/Enrollment and Study Evaluations

A study specific Subject Identification Number (SID) will be assigned in consecutive order after informed consent is obtained.

The following data will be collected:

- Patient demographics (at minimum Gender, Age and Race)
- Surgical Date
- Patient Pain Assessment
- Patient self-reported pre-existing conditions (list, if confirmed), if available
- OrthoCor Active System or SOC intervention use details
- Device information (serial number on OrthoCor Active System and OrthoPods)
- Concomitant Pain Medication Use
- Pregnancy Test Results

For those subjects that elect to participate in the research exploratory extension, the patient pain assessment will be collected for another 2 weeks. The extension data will be used for research and publication only.

OrthoCor Active System: Subject(s) are to apply a fully charged brace with a new set of OrthoPods over the affected area for a total of 2 hours at their first convenient opportunity each day. Subject(s) should be instructed to contact the site if they experience unusual sensations or discomfort during the use of the brace.

9.4 Study Exit

Subjects will be considered to have completed and exit the study after 14 consecutive days of OrthoCor Active System or SOC intervention use and the daily OrthoCor Patient Pain eDiary and relevant data is completed.

If significant improvement is noted in the subjects using the OrthoCor Active System after 32 subjects are enrolled into each treatment group, the study will be considered completed and all subjects will have the option to move into the research extension portion. The remaining subjects on SOC will have the ability to move into the active group even if they have not reached or have declined to participate in the research extension.

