9.5 Study Schedule of Assessments

In the evening of each day the subject should rate their pain using the provided scale and record their rating in the eDiary. Refer to Table 1 Schedule of Assessments.

Table 1. Schedule of Assessments

Assessments	Screening/Baseline (Day 0)	Day 1 - 14	Research Extension (if applicable) Day 15 – 30
Inclusion/Exclusion Criteria	X		
Demographics	X		
Surgical Date	X		
Pain Assessment	X	X	X
Self-reported Pre-Existing Conditions*	X*		
OrthoCor Active System/SOC Intervention Use		X	X
Device Information	X		
OrthoPod Information	X	X	X
Concomitant Pain Medication Use	X	X	X
Adverse Event, related to the test device		X	X
Pregnancy test for WOCBP	X		

* Information to be collected if available

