10.0 ADVERSE EVENTS

Adverse events (AEs) may occur during the study.

Each adverse event will be recorded in the corresponding subject's eDiary. Each adverse event will be assessed by the Investigator as to its relationship and level of relatedness to the investigational device and/or assessment. In addition, the Investigator will identify the date of onset, severity, and duration of the AE. All adverse events will be monitored until they are adequately resolved or explained. If an AE continues after the evaluation, the Sponsor and Investigator should discuss the need and/or methods for continued surveillance of the event.

The Investigator must submit to the Sponsor a report of any Serious Adverse Event (SAE), Serious Adverse Device Effect (SADE) or Unanticipated Adverse Device Effect (UADE) within 24 hours of knowledge of the event.

Sponsor Contact: [name]
 [contact]
 Email: [contact]

In addition, the Investigator will report adverse events to the reviewing IRB (as applicable) according to the local reporting requirements.

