10.2 Adverse Event Reporting

Adverse events occurring after the baseline assessment but after the study product use will be documented on the appropriate AE report form. All adverse events will be recorded from day 1 until a subject's participation in the trial is considered complete, i.e., at screen failure, completion of study participation (if applicable), subject's demise, or when a subject is discontinued / withdrawn.

It is the responsibility of the Investigators to inform their IRB of adverse events as required by their local IRB procedures.

Anticipated observations related to the study procedure will be tabulated but will not be categorized as adverse events unless they require mitigation by the treating physician or are greater in severity, duration or degree of incidence than anticipated.

Investigators must notify Caerus Corporation (or designee) within 72 hours of discovering any Unanticipated Adverse Device Events (UADE). Investigators are required to submit a report of a UADE to the reviewing IRB as soon as possible, but in no event later than 10

working days after the Investigator first learns of the event. UADEs must be documented as appropriate in the eDiary.

The Sponsor's evaluation of the UADE must be reported to the FDA, all reviewing IRBs, and participating Investigators within 10 working days of knowledge of the event by the Sponsor. All UADE will be reported to the FDA according to regulatory reporting requirements found in CFR 812.46.

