11.3 Handling Missing Data

Only subjects with non-missing data for the OrthoCor Active System or the SOC will be used in the statistical analysis, i.e., a complete case analysis.

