10. STUDY ASSESSMENTS

Mankoski Pain Scale assessments are conducted during the study for a period of 2 weeks of treatment with OrthoCor Active system or Standard of Care. The enrolled participant will have a treatment period from Day 0 through Day 14 when the study ends, and a research extension period and assessments are conducted for a period of additional 2 weeks (see Table 1. Schedule of Assessments in protocol).

The primary endpoints as well as safety analyses will be evaluated at study end.

Exploratory analyses will be assessed after the extension period of additional 2 weeks.

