12.4. Handling Missing Data

Only participants with complete available data will be used in the statistical analysis, i.e., a complete case analysis. For missing visits, an imputation of last visit carried forward will be considered.

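### Completion is defined by consecutive days of use and nothing keeps a subject who stops treatment in the eDiary to Day 14, so the primary comparison may be selective

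*Protocol*

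**What the plan says.** **Completion and exit.** Protocol 9.4: "Subjects will be considered to have completed and exit the study after 14 consecutive days of OrthoCor Active System or SOC intervention use", with the diary and other relevant data also complete. SAP 10 uses a calendar: "The enrolled participant will have a treatment period from Day 0 through Day 14 when the study ends".

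**Adverse events.** Protocol 10.2: "All adverse events will be recorded from day 1 until" the subject's participation is over. It then lists what ends participation: screen failure, completion, death, "or when a subject is discontinued / withdrawn". Protocol 10.0 adds: "All adverse events will be monitored until they are adequately resolved or explained".

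**Pain ratings.** Protocol 9.5: "In the evening of each day the subject should rate their pain using the provided scale and record their rating in the eDiary". Table 1 marks the pain assessment for Days 1 to 14 and attaches no condition of use. Protocol 9.0 plans a single on-site visit, so the later ratings are diary entries.

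**Analysis.** Protocol 11.3: "Only subjects with non-missing data for the OrthoCor Active System or the SOC will be used in the statistical analysis". SAP 12.4: "Only participants with complete available data will be used in the statistical analysis, i.e., a complete case analysis", followed by a statement that carrying the last visit forward will be considered. SAP 11.2 puts every enrolled subject with any treatment in the ITT set and requires two weeks of treatment only for the PP set. SAP 12.6 links the complete-case rule to the PP analysis and places all subjects in ITT.

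**Timing.** Protocol 9.2 starts assessment at once after consent and eligibility. Protocol 15.2 has the device reach the participant in 3 to 5 days.

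**The concern.** Stopping treatment and leaving the study are different events, and the plan does not separate them. A subject may stop because of no relief, because of irritation or because the pain has gone. Each reason is related to the outcome. If such subjects leave the diary when they stop, the Day-14 comparison is made among those who carried on, not between the groups as allocated.

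The trial is open label, so the decision to stop can also depend on knowing the assignment. The primary safety endpoint covers two weeks of device use, and events that begin after a stop could fall outside recording. An analysis can only make assumptions about ratings that were never collected.

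**Working it through.** The plan gives no figure for stopping, adherence or the SD of the pain change, so there is nothing to reproduce. The check is a reading of the text, then an illustration of size.

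**1. Which clock governs.** Protocol 9.4 counts consecutive days of use; SAP 10 counts calendar days. They agree only for a subject who starts on time and never misses a day. Neither document says which rule applies after a missed day or an early stop.

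**2. What happens to a subject who stops.**
- *Pain:* Protocol 9.5 and Table 1 schedule ratings to Day 14 whatever the use. Nothing says that ratings end at a stop, and nothing tells the subject or the site to continue.
- *Adverse events:* Protocol 10.2 ends recording with participation and names discontinuation as one such end. The term is undefined, so a site could apply it to stopping treatment or to leaving the trial. Under Protocol 10.0 a known event is still followed, but that sentence does not cover a new event.

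**3. What the analysis does with a missing Day-14 rating.** Protocol 11.3 and SAP 12.4 exclude the subject, while SAP 12.6 keeps everyone in ITT. The sections conflict, and ITT membership does not supply a rating that was not taken. Carrying the last value forward is only to be considered, and for someone who left the diary at the stop it would use a rating from no later than the stop.

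**4. Illustrative size.** Let *d* be the share of the device arm missing from the analysis, *m* the mean improvement of those kept, and *g* how much smaller the improvement is in those lost.
- Whole-arm mean = (1 − d)·m + d·(m − g) = m − d·g.
- Analysed mean = m, so the overstatement is d·g.
- With loss in both arms, the between-arm shift is d·g in the device arm minus d·g in the SOC arm. It is about zero if loss and prognosis are equal, and it is reversed if those lost did better (g negative).

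Inputs: 50 per arm (SAP 7) and alpha 0.05 (SAP 11.1; two-sided testing is assumed). The other inputs are assumptions: no true difference, loss only in the device arm, g = 1 to 3 points, SD 2.0 to 2.5 points, normal approximation. The standard error is SD·√(1/50 + 1/(50(1 − d))).

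| d | shift d·g (points) | two-sided type I error |
|---|---|---|
| 10% | 0.1 to 0.3 | 0.054 to 0.113 |
| 20% | 0.2 to 0.6 | 0.066 to 0.293 |
| 30% | 0.3 to 0.9 | 0.085 to 0.533 |

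One cell worked: for d = 20%, g = 2, SD = 2.0, the shift is 0.4 and the standard error is 2.0·√(1/50 + 1/40) = 0.424. The ratio is 0.943, and the type I error is 1 − Φ(1.96 − 0.943) + Φ(−1.96 − 0.943) = 0.156.

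**5. Delivery.** Suppose enrolment is Day 0, the 3 to 5 days run from enrolment, and use starts on the day of receipt (all assumptions). Then the days of use possible by Day 14 are 14 − 3 + 1 = 12 down to 14 − 5 + 1 = 10. On that count a device subject could not reach 14 consecutive days within the SAP's calendar.

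**The case against.** The strongest reply is that the documents do not say what a worried reader might infer from them.

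- *That a subject who stops loses the Day-14 pain score by rule.* No section says so. The diary schedule is by calendar day, and Protocol 10.2 concerns adverse events and can naturally be read as leaving the trial. This stands: the loss is a risk left open by silence, not a stated rule.
- *That pausing for a day costs the outcome.* This is not supported. A pause affects completed status under 9.4, and no analysis set in SAP 11.2 uses that status. With assumed independent daily adherence of 0.98 or 0.95, the chance of 14 unbroken days is 0.98^14 = 75% or 0.95^14 = 49%. Those figures describe the 9.4 label and do not measure lost data.
- *That the harm which led to stopping goes unrecorded.* This is not supported. Such an event begins before the stop, is followed under Protocol 10.0, and belongs to a subject in the safety population, which has no completion condition. Only events starting later are exposed.
- *That the comparison necessarily favours the device.* This is not shown. The exit rule covers both arms, and subjects whose pain has gone may also stop, which would push the other way.

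ITT is also defined without an adherence condition, and carrying values forward is mentioned. Both soften the problem on paper. Neither tells anyone to collect the missing ratings, and the complete-case wording in Protocol 11.3 and SAP 12.4 still excludes subjects without them.

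**Conclusion.** The gap in the text is clear. Completion follows use in one document and the calendar in the other, discontinuation is undefined, and no provision keeps a subject in the eDiary after treatment stops. The consequence is conditional: such subjects may be missing from the primary comparison, and adverse events that begin after the stop may be missed.

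Bias in favour of the device is plausible but not certain. The range of 0.1 to 0.9 points holds only if 10% to 30% of the device arm is lost with changes 1 to 3 points worse and there is no matching loss under SOC. None of these inputs comes from the documents. The point is worth acting on because the change is cheap and must be made before the data are due. The sections on the start of assessment, device delivery, exit and the treatment period also need to be reconciled.

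**What to change.** - **Protocol 9.4:** define study completion as Day 14 of a clearly anchored 14-day period, whatever the use. State what Day 0 is, and reconcile it with Protocol 9.2, Protocol 15.2 and SAP 10.
- **Protocol 9.4 and 9.5:** state that subjects who stop or interrupt the device or SOC without withdrawing consent keep entering pain ratings, pain medication and adverse events in the eDiary to Day 14. Record the stop date and reason.
- **Protocol 10.2:** make clear that adverse-event recording ends at Day 14 (or at the end of the extension) or at withdrawal of consent, not at stopping treatment.
- **SAP 12.4 and 12.6:** use ratings made after a stop in the ITT analysis, and resolve the conflict between the complete-case rule and including all subjects. Keep the adherence condition in the PP set only, as SAP 11.2 already does.

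These changes concern data collection and analysis, not how subjects are treated. The cost is protocol and SAP wording, an eDiary entry for stop date and reason, some extra reminders to subjects off treatment, and an ITT effect that may be slightly less favourable.

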11.0 STATISTICAL ANALYSIS

The primary effectiveness endpoint of this study is the change from baseline of the OrthoCor Active System compared to the SOC intervention results after 14 days.

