11.4 Interim Analysis

No interim analyses are planned for this study.

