11. GENERAL CONSIDERATIONS

11.1. General Methods

A repeated measures ANOVA will be utilized to assess statistical differences between the active and sham devices. A test of normality will be performed. If the data is not shown to be normally distributed, nonparametric methods may be used. All hypotheses are performed at an alpha equal to 0.05.

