11.3. Timing of Analyses

The final analysis will be performed after all enrolled participants have completed the 2 weeks treatment period.

The additional analysis for exploratory research will be performed after all enrolled participants completed the 2 weeks of treatment and any of the additional exploratory days and up to 2 weeks.

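### Protocol 9.4 ends the study on an undefined 'significant improvement' after 32 per group are enrolled, while 11.4 plans no interim analysis and no alpha is allocated

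*Protocol*

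**What the plan says.** Protocol 9.4 (Study Exit) sets a condition: "If significant improvement is noted in the subjects using the OrthoCor Active System after 32 subjects are enrolled into each treatment group". If it is met, "the study will be considered completed and all subjects will have the option to move into the research extension portion". It adds: "The remaining subjects on SOC will have the ability to move into the active group even if they have not reached" the extension or have declined it.

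Protocol 11.4 (Interim Analysis) states: "No interim analyses are planned for this study".

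Protocol 11.0 gives the primary effectiveness endpoint as "change from baseline of the OrthoCor Active System compared to the SOC intervention results after 14 days". Protocol 9.2 defines the counting unit used in 9.4: "A study participant is considered enrolled after they have signed an informed consent form and after the inclusion/exclusion criteria have been met".

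The SAP describes a final analysis and a later exploratory one. On timing, 11.3 says "The final analysis will be performed after all enrolled participants have completed the 2 weeks treatment period". On error control, 11.1 says "All hypotheses are performed at an alpha equal to 0.05". SAP Section 7 plans up to 50 subjects per arm. The SAP does not mention 32 per group, a stopping boundary, alpha spending, or who would look at the data.

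**The concern.** Ending a study because of an observed efficacy result is an interim efficacy analysis, whatever it is called. Sections 9.4 and 11.4 therefore contradict each other, and the SAP, which should settle the matter, is silent.

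The trigger is also open to two readings with different consequences:

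- **Between-arm test.** It is an unadjusted extra look at the primary comparison, and type I error rises above the planned 5%.
- **Within-arm change.** The wording refers only to improvement among device users, so a change from baseline in that arm would satisfy it. That does not test the primary endpoint. Improvement shared by both arms can then end the study early and cost the primary comparison its power.

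Under either reading the count is of subjects who have consented and are eligible, so the last ones counted have no Day-14 score. The trial is open label, so the definition could be settled after results have been seen. Remaining SOC subjects may also move to the device before Day 14. That affects the comparator arm only, and neither document says how scores recorded after a move are analysed.

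**Working it through.** The plan gives no figure for the error rate or power of this rule, and no derivation of 32, so there is no stated figure to reproduce.

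**Inputs from the documents.** 32 per group at the trigger (Protocol 9.4); up to 50 per arm (SAP 7); alpha 0.05 for every hypothesis, sidedness not stated (SAP 11.1).

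**Assumptions.** Two-sided 0.05 tests (critical value c = 1.96); one look; then one test at 50 per arm. The documents give no SD or effect size, so effects are in SD units of the change score.

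**Reading 1: between-arm test, with the look itself decisive.** If all 32 per arm have Day-14 data, the information fraction is t = 32/50 = 0.64. Under the null, Z1 (look) and Z2 (final) are standard bivariate normal with correlation √0.64 = 0.80.

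- Stop in either direction: P(|Z1| > c or |Z2| > c) = 0.0781.
- Stop only for the device: P(Z1 > c) + P(Z1 ≤ c, |Z2| > c) = 0.0250 + (0.0140 + 0.0250) = 0.0640.
- Claims favouring the device: P(Z1 > c or Z2 > c) = 0.0250 + 0.0140 = 0.0390, against 0.025.

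| Information at look | Either direction | Device only | Favouring device |
|---|---|---|---|
| 0.30 | 8.9% | 7.0% | 4.5% |
| 0.64 | 7.8% | 6.4% | 3.9% |
| 0.80 | 7.1% | 6.0% | 3.5% |

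Section 9.4 does not limit the number of looks. Re-testing after every further pair from 32 to 50 per arm gives about 11.6% (simulation, two-sided, either direction).

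**Reading 2: within-arm test, with no device effect over SOC.** The trigger is a one-sample t-test on the device arm, n = 32, two-sided 5%, noncentrality d√32. The between-arm error comes from simulation (400,000 trials per case): stop at 32 per arm if the device-arm change is significant, otherwise continue to 50, then run one between-arm t-test at 0.05.

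| Common improvement (SD) | Study stops early | Between-arm type I error |
|---|---|---|
| 0.3 | 38% | 5.1% |
| 0.5 | 78% | 4.8% |
| 0.8 | 99% | 4.9% |

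The stops are early completions, not false claims.

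**Power lost by stopping.** Two-sample t-test, noncentrality d√(n/2):

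| True difference (SD) | 32 per arm | 50 per arm |
|---|---|---|
| 0.5 | 50% | 70% |
| 0.8 | 88% | 98% |

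**Boundaries that would hold 5%.** Lan-DeMets O'Brien-Fleming-type spending at t = 0.64:

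| How alpha is spent | z at look, end | Nominal two-sided p at look, end |
|---|---|---|
| 0.025 per side | 2.570, 1.988 | 0.0102, 0.0468 |
| Total 0.05 | 2.450, 2.008 | 0.0143, 0.0447 |

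**The case against.** The strongest objection is that the look need not be the decisive test. Section 9.4 says only that the study is considered completed, and SAP 11.3 places the final analysis after everyone enrolled has finished two weeks. On that combination a positive look stops enrolment, and the primary test is then run on all 32 per arm. With Day-14 data on 16, 20, 24 or 28 of the 32 at the look, and stopping only for the device, overall type I error is 5.3%, 5.4%, 5.5% or 5.7%. Claims favouring the device run from 2.8% to 3.2%. If the look can stop in either direction, the overall error is 5.6% to 6.5%. In this scenario less data at the look means less inflation. The calculation is right, and it shows that the 6.4% and 7.8% depend on a decisive look. It still exceeds 5%, and it needs SOC subjects to finish as assigned, which the early-move sentence undermines.

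Three further points have some force:

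- SAP 7 frames the study as non-inferiority on a binary response, while the figures here use two-sided tests of difference. The SAP does not settle sidedness. With one-sided 0.05 at both looks, the error is 7.5% against 5%, so the direction of the conclusion does not change.
- The plan says up to 50 per arm, so 50 is a ceiling. That permits a smaller study, but it does not cover a stop that depends on the result.
- The number of SOC subjects who would move early is unknown, so that part of the concern has no size attached.

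**Conclusion.** The concern holds and has to be resolved. The contradiction between 9.4 and 11.4, the undefined trigger and the missing alpha are plain from the text and need no assumptions.

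The size depends on the reading. A single between-arm look gives an overall type I error from about 5.3%, if it only halts enrolment and subjects finish as assigned, to 6.4% or 7.8% if it is decisive with full Day-14 data on 32 per arm. More looks raise it. Under the within-arm reading there is no material alpha inflation. The damage is early stopping on improvement unrelated to the device and a loss of up to 20 percentage points of power (70% to 50%) in the cases examined. As written, the error rate of the primary test cannot be established.

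**What to change.** Choose one of two routes:

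1. Delete the completion rule at 32 per group from Protocol 9.4, so that it agrees with 11.4.
2. Declare the look in Protocol 11.4 and the SAP as one formal interim: a between-arm test of the primary endpoint when 32 per arm have Day-14 data, with a named alpha-spending boundary. For Lan-DeMets O'Brien-Fleming-type spending at information 0.64, state which nominal pair applies: 0.0102 then 0.0468 (per side), or 0.0143 then 0.0447 (total alpha). Say who carries out and sees the look.

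Under either route, reconcile the early-move sentence in 9.4 with the Day-14 endpoint, and state in the SAP how scores recorded after a move enter the primary analysis.

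The cost is mainly wording in two documents, with IRB approval of the amendment under Protocol 14.1. Deleting the rule gives up the informal early stop, which means up to 100 − 64 = 36 more subjects than stopping at 32 per arm, still within the planned 100. A formal look needs a data cut and lowers the final nominal alpha by 0.05 − 0.0468 ≈ 0.003 or 0.05 − 0.0447 ≈ 0.005.

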8.3 Subject Population

The target population for this measurement consists of both males and females, presenting to the designated study sites with pain in superficial soft tissue, such as in the ankle, back, knee, wrist, elbow, shoulder, foot, or neck who are prescribed the use of the OrthoCor Active System or Standard of Care (SOC) intervention.

Eligible subjects must meet the inclusion and exclusion criteria described in Sections 8.4 and 8.5. Any questions from the investigative site regarding a potential subject's eligibility for enrollment must be discussed with the Sponsor (or designee) prior to consenting and enrolling the subject into the study for the investigational measurement.

It is estimated that up to 100 subjects may be enrolled into the study.

Patients will be enrolled consecutively at each participant site until up to 50 using the OrthoCor Active System and up to 50 using the Standard of Care (SOC) intervention have enrolled. The CRO will stratify the arms (OrthoCor Active System vs SOC) by selecting the arm alternatively. The patients will be enrolled consecutively at the participant site until enrollment is met.

As part of exploratory research extension, patients using the OrthoCor Active system will have the opportunity to continue on the trial for an additional 2 weeks. Participants assigned SOC have the opportunity to cross-over using the OrthoCor Active system for the additional 2 weeks. Participation in the exploratory extension is optional.

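### If the 32-per-group trigger in Protocol 9.4 is met, standard-of-care (SOC) subjects may move to the device before Day 14, and neither document says how they enter the primary comparison

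*Protocol*

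**What the plan says.** The first paragraph of Protocol 9.4 defines completion: "Subjects will be considered to have completed and exit the study after 14 consecutive days of OrthoCor Active System or SOC intervention use", with the diary complete.

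The second paragraph sets a condition, "If significant improvement is noted in the subjects using the OrthoCor Active System after 32 subjects are enrolled into each treatment group". If it is met, the study counts as finished and every subject may enter the research extension. The paragraph then adds: "The remaining subjects on SOC will have the ability to move into the active group even if they have not reached or have declined" that extension.

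Other sections put the crossover later:

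- Protocol 8.3: "Participants assigned SOC have the opportunity to cross-over using the OrthoCor Active system for the additional 2 weeks". SAP 4 and 6 say the same.
- Protocol Table 1 heads the extension column "Research Extension (if applicable) Day 15 – 30".
- SAP 11.3: "The final analysis will be performed after all enrolled participants have completed the 2 weeks treatment period".

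The primary endpoint in Protocol 11.0 is "the change from baseline of the OrthoCor Active System compared to the SOC intervention results after 14 days".

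**The concern.** The primary contrast needs a Day-14 score obtained on SOC alone. Once the trigger is met, 9.4 gives SOC subjects, and only them, the option of leaving SOC before that score exists. The subject makes the choice, in an open-label trial, after a favourable device result.

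The SAP does not say which arm such a subject belongs to or what happens to ratings made after the switch. Three analysts could handle this in three ways:

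- Drop the switchers. The control arm then selectively loses subjects who wanted the device.
- Keep their Day-14 rating under SOC. A rating made after device use is then counted as a control result.
- Count them as device subjects. Allocation is then broken, and the device arm gains people with shortened use and a baseline that preceded a period on SOC.

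**Working it through.** **Step 1. Does 9.4 reach back before Day 14?** The move is open to SOC subjects who have not reached the extension. The extension starts at Day 15, so these subjects have not finished 14 days on SOC. The trigger counts subjects enrolled, not subjects who have completed, so the most recent may be close to Day 0. The answer is yes, if the trigger is met.

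**Step 2. Does any analysis rule cover a switcher?**

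| Section | Rule | Effect on a pre-Day-14 switcher |
|---|---|---|
| SAP 11.2 and 12.6, ITT | All enrolled with any treatment; all subjects | Included, but the arm is not stated |
| SAP 11.2, PP | 2 weeks of treatment, no critical data missing | Unclear; it does not say 2 weeks of one treatment |
| Protocol 11.3, SAP 12.4 | Complete cases; carry-forward only a possibility | Dropped, carried forward from SOC days, or scored after device use |
| SAP 11.3 | Analysis after all enrolled finish 2 weeks | Cannot be met on SOC alone |

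No rule settles the matter.

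**Step 3. How many could be affected?** The plan gives no figure to reproduce, so this is an illustration.

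Inputs from the documents: up to 50 SOC subjects, a study duration of 3-5 months (taken as 90-150 days), a 14-day treatment period, and 32 per group at the trigger. Assumptions: accrual is even, and the look occurs when the 32nd SOC subject enrols.

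SOC subjects inside their 14 days = (50 / accrual days) × 14.

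- Accrual over the whole duration: 50/150 = 0.333 per day, × 14 = 4.7; 50/90 = 0.556 per day, × 14 = 7.8. That is 15-24% of 32.
- Accrual over the duration less 14 days of follow-up: 50/136 = 0.368 per day, × 14 = 5.1; 50/76 = 0.658 per day, × 14 = 9.2. That is 16-29% of 32.

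Together this is about 5 to 9 subjects.

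Protocol 15.2 says a device arrives in 3 to 5 days. If that also holds for switchers, only those in about their first 14 − 5 = 9 to 14 − 3 = 11 days could use it before Day 14:

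- Whole-duration rates: 0.333 × 9 = 3.0 to 0.556 × 11 = 6.1 subjects (9-19% of 32).
- Shorter accrual window: 0.368 × 9 = 3.3 to 0.658 × 11 = 7.2 subjects (10-23%).

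**Step 4. What would that do to the contrast?** Suppose a fraction f of the SOC arm switches, is analysed as SOC, and shows the full device effect by Day 14. The expected difference is then multiplied by (1 − f). With 32 per arm, two-sided 0.05 and an assumed standardised effect d:

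- Kept in SOC: power = Φ(d(1 − f)/√(2/32) − 1.96).
- Dropped: power = Φ(d/√(1/32 + 1/(32(1 − f))) − 1.96).

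| d (assumed) | No switchers | Kept, f = 16% to 29% | Dropped, f = 16% to 29% |
|---|---|---|---|
| 0.8 | 89% | 77% to 62% | 86% to 83% |
| 0.5 | 52% | 39% to 30% | 48% to 45% |

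These are upper-end figures, because every eligible subject is assumed to switch. The dropped column shows lost precision only. It does not include bias from who chooses to leave.

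**The case against.** The strongest reply is that 9.4 declares the study finished once the trigger is met, so the move is post-study access. A subject still inside the 14 days would have no Day-14 score at that look, switch or no switch. This would be a full answer if the documents fixed a data cut-off at the look. They do not, and SAP 11.3 still waits for all enrolled participants.

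Several other points stand:

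- A reader might infer that part of the control arm will certainly lack an SOC-only score. The text does not support that, because the option is conditional on the trigger and voluntary.
- A reader might infer that the plan counts switchers as device subjects. The wording about moving into the active group allows that reading, but no analysis section adopts it.
- Protocol 9.3 restricts extension data to research and publication. That partly deals with post-switch ratings, but not for someone who switches without entering the extension.
- Pain is rated daily and the planned analysis is repeated-measures, so a switcher's earlier SOC ratings exist and need not be lost. Carry-forward would also use the last SOC rating, but the SAP only says it will be considered.
- If the look waits for 32 completers while enrolment continues, the in-period subjects are additional to the 32, and dropping them leaves 32.

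**Conclusion.** The point holds in conditional form. If the trigger is met, SOC subjects inside their 14 days may move to the device, and part of the control arm may have no SOC-only Day-14 score. That contradicts Protocol 8.3, SAP 4 and 6, the completion definition in the first paragraph of 9.4, and SAP 11.3. No analysis rule resolves it.

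The size cannot be derived from the documents. Under even accrual and a look at 32 enrolled per group, about 5 to 9 of 32 SOC subjects would be in their treatment period. About 3 to 6 could use the device before Day 14 if the stated delivery time applies (up to 7 with the shorter accrual window). The number is zero if the trigger is not met, if the look waits for Day 14, or if nobody switches. No single percentage should be quoted as the expected loss.

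It still needs fixing before results are seen: any effect is confined to the control arm, is self-selected, and falls on the primary comparison. How the 32-per-group trigger is to be tested, given that Protocol 11.4 plans no interim analysis, is a separate matter.

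**What to change.** **Protocol.** Reconcile the second paragraph of 9.4 with its first paragraph, with 8.3 and with SAP 4, 6 and 11.3 on two matters: whether an SOC subject can change treatment before the Day-14 rating, and which data cut-off applies to the primary analysis if the trigger is met. The crossover rule itself is for the sponsor to decide.

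**SAP 11.2, 12.1 and 12.4.**

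- Analyse every subject in the allocated arm, and never count a switcher as a device subject in the 14-day comparison.
- Record the date of any switch.
- Keep switchers' pre-switch daily SOC ratings in the repeated-measures analysis. Setting post-switch ratings aside under a complete-case rule would drop these subjects and recreate the selective loss. A repeated-measures ANOVA that requires every rating would drop them too, so the model must accept incomplete series (for example, a mixed model for repeated measures).
- Add a sensitivity analysis that uses switchers' observed Day-14 ratings in the allocated arm.
- Report the number who switched before Day 14.

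**Cost.** A few sentences across the two documents, one date field and a little more analysis work. Use of the intervention is already collected on Days 1-14, so the switch date may be partly captured.
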